Note: Preferred order of assessments at all timepoints: , VAS-L, VAS-A, vital signs (temperature [°C], respiratory rate, heart rate, and blood pressure),

- ^a The EOS Visit will be conducted at the time of discontinuation if this occurs at any time before Day 7±1 day.
- ^b All predose assessments must be completed prior to IP administration.
- ^c Safety laboratory tests will include hematology, serum chemistry, and urinalysis at all scheduled time points.
- ^d Urine pregnancy test at all scheduled time points.
- ^e Heart rate and blood pressure to be collected in semi-inclined position at all scheduled time points. Predose (Hour 0) vital signs will be collected within 60 minutes prior to dosing.
- f Drug and alcohol testing will occur prior to dosing on Day 1(see Section 12.1.6 for a list of analytes). Drug testing will be on a urine specimen via urine dipstick. Alcohol use will be tested either on a urine specimen dipstick or breath test. Participants with a failed drug or alcohol test on Day 1 are excluded from participation in the study.
- g ECGs must be performed after the participant has been in a supine position for at least 5 minutes.

for both VAS-L and VAS-A will be done twice daily, once each in the morning and evening, on Day 2 through Day 6 and on the morning of Day 7.

The participant will be contacted by the site on Day 2 through Day 6 to remind them to begin remote assessments.

^mContinuous pulse oximetry to occur for the duration of the infusion. Oxygen saturation should be recorded prior to dose escalation at 0.5 hour and 1 hour. Otherwise, it need only be recorded in the event of confirmed hypoxia, in which case, the event is to be recorded as an AE.

^o If deemed medically appropriate by the investigator, participants will be released from the clinic after the 2-hour safety assessments have been completed. Participants will be cautioned against engaging in potentially hazardous activities requiring mental alertness, including driving, until any sedative effects have dissipated A designated companion must drive the participant when they are discharged from the clinic.

- ^p A phone call to follow up on any AE(s) will be conducted, if deemed appropriate by the investigator, to review the current status of the participant.
- ^q All changes to any medication should be captured. Participants will be asked about any changes during clinic visits.

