13.3. General Considerations

All participant data, including those that are derived, that support the tables and figures will be presented in the participant data listings. Some data may be presented only in participant listings, whereas other data may be presented in both listings and corresponding table(s) or figure(s).

For the Screening period and Days 2-7, not more than one (1) set of remote morning VAS components and one (1) set of remote evening VAS components per timepoint will be used in the statistical analysis of data for a given study participant. However, morning and evening VAS component data may be displayed and descriptively summarized.

For in-clinic VAS component assessments (VAS-A and VAS-L, Section 11.1.2), baseline is defined as the most recent VAS component value immediately prior to the start of IP infusion.

For remote daily VAS-A assessments, baseline is defined as the arithmetic mean of Screening VAS-A values per participant; likewise, for remote daily VAS-L assessments, baseline is defined as the arithmetic mean of Screening VAS-L values per participant.

Continuous data will be summarized, at minimum, with number (n), mean, standard deviation (SD), median, Q1, Q3, minimum, and maximum. Categorical data will be summarized, at minimum, with counts and percentages. Change from baseline is calculated as the baseline value minus the post-baseline value, unless defined otherwise for specific assessments and/or endpoints.

Summary tables will generally summarize values at each timepoint and change from baseline at each post-baseline time point.

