13.5. Efficacy Analysis

Efficacy analyses will primarily be based on the Efficacy Set.

The two secondary endpoints of this study are (a) tinnitus perception during brexanolone infusion based on the VAS and (b) tinnitus perception after brexanolone infusion based on VAS. For remote assessments, ratings for both VAS-L and VAS-A will be obtained twice daily, once each in the morning and evening, during the both the Screening Period and on Day 2 to Day 7.

The daily arithmetic means of remote VAS-A and VAS-L ratings obtained during the Screening Period will be computed and used descriptively. The daily arithmetic means of remote VAS-A and VAS-L ratings obtained on Days 2-7 will be used both descriptively and in statistical modeling.

Each component of VAS for tinnitus will have change from baseline score (see Section 13.3 for a description of appropriate baseline for a given schedule of assessment timepoint) at each postbaseline assessment (whether during brexanolone infusion or post-brexanolone infusion) computed. Descriptive statistics of both VAS component scores and VAS component change from baseline scores will be summarized.

Each VAS component score will be analyzed separately for each secondary endpoint. This will be done separately for Day 1 (ie, during treatment) and Days 2 to 7 (ie, after treatment). The during-infusion Day 1 VAS component data will consist of VAS components obtained at 0.5, 1, 2, 3, 4, 5, and 6 hours. The post-infusion Days 2 to 7 VAS component data will consist of daily arithmetic component means.

Each analysis will utilize a mixed effects model for repeated measures. Each repeated measures model will include (a) the change from baseline score of the appropriate VAS component as the dependent variable and (b) both baseline VAS component value and visit as fixed effect independent variables. Participants will be treated as random effects.

Model- based point estimates (ie, least squares means, their 95% confidence intervals, and associated p-values) at each time point (visit) will be reported where applicable. Line plots of change from baseline scores will be plotted with standard error bars. Additional analyses will be detailed in the SAP.

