9.1. Visual Analog Scales

The VAS-L and VAS-A are participant-rated scales for evaluating tinnitus (Adamchic et al 2012). Scoring for both is along a linear horizontal scale, with the left side anchor (score of 0) representing the lowest severity and the right side anchor (score of 100) representing the highest severity of the rated tinnitus experience. Intermediate scores are determined by extrapolation between the two sides of the scales.

To assess tinnitus loudness (VAS-L), participants will answer the question "How loud is your tinnitus now?" on a horizontal scale anchored on left by "not audible" and on right by "extremely loud". To assess tinnitus annoyance (VAS-A), participants will answer the question "How much is your tinnitus annoying you now?" on a horizontal scale anchored on left by "not annoying" and on right by "extremely annoying".

The VAS-L and VAS-A will be administered both as remote and as in-clinic measures at different times of this study. Remote VAS data collection will occur from Day -7 to Day -1 (preinfusion) and from Day 2 to Day 7 (postinfusion). For remote assessments, ratings for both VAS-L and VAS-A will be obtained twice daily, once each in the morning and once in the evening. And the daily arithmetic means of VAS-L and VAS-A ratings will be computed separately for remote measures obtained during pre- and postinfusion periods. -. For remote assessments, the daily arithmetic mean will be calculated by averaging the morning and evening scores ([morning score + evening score] / 2). If a participant is missing either a morning or evening score, then the single available score will be used as the mean for that day.

The VAS-L and VAS-A will be obtained in-clinic during the treatment period (Day 1), administered once prior to start of infusion and then repeated at hours 0.5, 1, 2, 3, 4, 5 and 6 of the infusion.

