For the treatment period (Day 1), baseline is defined as the most recent value immediately prior to the start of IP infusion, or predose. For the postinfusion remote assessment period (Days 2 through 7), baseline is defined as the average of all available preinfusion values per participant collected from Day -7 through Day -1. This will be calculated by summing the daily arithmetic means and dividing by the total number of non-missing days. If a participant is missing either a morning or evening score, then the single available score will be used as the mean for that day Missing day or partial missing day VAS ratings will not be imputed.

Descriptive statistics of both VAS component scores and VAS component change from baseline scores will be tabulated. Considering the small sample size, unbiased Hedge's g will be used to compare the effect size of the post baseline score at each timepoint to the baseline score. Hedge's g will be calculated for pre-post scores in one group using the following formula:

$$g = d \times J$$
 Where $d = \frac{(post-baseline\ mean)-(baseline\ mean)}{SD_{within}}$ and $J = 1 - \frac{3}{4(2n-2)-1}$

SD_{within} can be computed from the standard deviation of the change from baseline (SD_{CFB}) as

$$SD_{within} = SD_{CFB}/\sqrt{2(1-r)},$$

r is the correlation between baseline and post-baseline, n is the number of pairs.

The 95% CI of Hedge's g will be calculated as

$$g \pm t(n-1, 0.025) \times SE(g);$$

Where
$$SE(g) = \sqrt{Var(g)} = \sqrt{Var(d)} \times J^2 = \sqrt{\left(\frac{1}{n} + \frac{d^2}{2n}\right)2(1-r)} \left(1 - \frac{3}{4(2n-2)-1}\right)^2$$

(Borenstein et al 2009).

[figure not shown]
Each VAS component score will be analyzed separately; this will also be done separately for Day 1 (during treatment) and Days 2 to 7 (after treatment).

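### The documents disagree on how often and where VAS is rated on Day 7; a remote morning-only rating would be compared with a morning-plus-evening baseline.

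*SAP*

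**What the plan says.** **Frequency on Day 7.** The VAS footnote to Protocol Table 3 schedules ratings morning and evening "on Day 2 through Day 6 and on the morning of Day 7". The footnote in SAP Appendix B carries the same words. The opening of each footnote is cut off in the text available, but the part about Day 7 is intact. Protocol 13.5 instead has ratings "once each in the morning and evening, during the both the Screening Period and on Day 2 to Day 7". SAP 9.1 includes Day 7 in remote collection and describes remote ratings as twice daily, with no exception for Day 7.

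**Setting on Day 7.** Protocol 7.1 and SAP 4.1 place remote follow-up on Days 2 to 6 and a clinic End of Study visit on Day 7 ± 1. The SAP Appendix B schedule marks a VAS at that visit.

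**Daily value.** SAP 9.1 averages the morning and evening scores. If one is missing, "then the single available score will be used as the mean for that day".

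**Baseline.** SAP 9.1: "For the postinfusion remote assessment period (Days 2 through 7), baseline is defined as the average of all available preinfusion values per participant", from Day -7 through Day -1. "This will be calculated by summing the daily arithmetic means and dividing by the total number of non-missing days". Protocol 13.3 is similar for remote ratings: "baseline is defined as the arithmetic mean of Screening VAS-A values per participant", with the same rule for VAS-L. For in-clinic ratings, Protocol 13.3 and SAP 7.2.1 use the last value before the infusion.

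**Use of Day 7.** SAP 9.1 models Days 2 to 7 with day as the repeated timepoint and computes Hedges' g at each timepoint.

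**The concern.** A change score should compare like with like. On Days 2 to 6, with complete ratings, the daily value and the baseline each give equal weight to morning and evening. Under the footnotes, the Day 7 value is a morning score alone, yet SAP 9.1 gives it the same baseline. If tinnitus is typically rated differently in the evening than in the morning, part of the Day 7 change is a time-of-day difference and not a change since baseline.

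Day 7 is the last follow-up point, so it bears on whether any post-infusion change persists. The study has one arm, so no control group cancels such an offset, and more participants would not remove it. If the rating is taken in clinic, the reader cannot tell which of two baseline rules applies.

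**Working it through.** **1. Count of ratings.** Baseline: 7 days × 2 = 14, which reproduces the 14 remote assessments stated in Protocol 7.1 and SAP 4.1. Post-infusion ratings per scale:

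| Source | Ratings |
|---|---|
| Schedule footnotes | 5 × 2 + 1 = 11 |
| Protocol 13.5, SAP 9.1 | 6 × 2 = 12 |
| Protocol 7.1, SAP 4.1 (remote only) | 5 × 2 = 10 |

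The footnotes can be read together with the design sections (Day 7 as one rating at the visit). Neither fits twice-daily ratings through Day 7.

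**2. Offset if Day 7 is remote and morning-only.** Let M be the mean morning score, E the mean evening score and D = E − M, with no drug effect. Changes are post minus baseline, as in SAP 7.2.1.

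- Complete baseline = (M + E)/2 = M + D/2.
- Days 2 to 6: (M + D/2) − (M + D/2) = 0.
- Day 7: M − (M + D/2) = −D/2.

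D is not in the documents. Over an assumed range:

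| D | −20 | −10 | 0 | +10 | +20 |
|---|---|---|---|---|---|
| Day 7 error (points) | +10 | +5 | 0 | −5 | −10 |

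Positive D makes Day 7 look better and negative D makes it look worse.

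**3. Incomplete baseline.** Dosing requires at least 10 of the 14 ratings. I applied the SAP rule to all C(14,4) = 1001 patterns of four missed ratings. The evening weight in the baseline has mean 0.500, SD 0.131, minimum 3/14 = 0.214 and maximum 11/14 = 0.786. Each extreme arises in C(7,4) = 35 patterns (35/1001 = 3.5%). One participant at the minimum can therefore be off by −0.21D to −0.79D. SAP section 12 expects about 10 dosed. If all 10 are at the minimum and misses are unrelated to time of day, the mean weight is 0.5 ± 1.96 × 0.131/√10 = 0.42 to 0.58. For D = ±10 the error is 4.2 to 5.8 points in size.

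**4. Hedges' g at n = 10.** J = 1 − 3/(4 × 18 − 1) = 0.958. The shift is −(D/2)/SD_within × J. For D = ±10 and an assumed SD_within of 15, 20 or 25, it is 0.32, 0.24 or 0.19 in size.

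**5. Price of a morning-only baseline.** Assume independent rating noise with equal variance. With complete ratings, the SD of the Day 7 change rises by √[(1 + 1/7)/(1 + 1/14)] = 1.033. Over the 1001 patterns the ratio averages 1.042. Its maximum, 1.095, occurs when 3 mornings and 7 evenings remain: √[(1 + 1/3)/(1 + 5.5/49)], where 5.5/49 = (3 × 0.5 + 4 × 1)/49. At least 10 − 7 = 3 mornings always remain, taking each assessment to include both scales.

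**6. If Day 7 is an in-clinic rating.** Protocol 13.3 and SAP 7.2.1 point to the predose value, while SAP 9.1 assigns Days 2 through 7 the diary average. The formula in step 2 cannot be applied until one rule is chosen.

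**The case against.** The strongest reply is that the bias is hypothetical. No document gives a morning-evening difference, so the point and g shifts above show sensitivity only. That stands.

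The reach is also small. Day 7 is one of six days of a secondary endpoint, the primary endpoint is the incidence of TEAEs, and no visible decision rule rests on Day 7. Raw scores are listed, and Protocol 13.3 allows "However, morning and evening VAS component data may be displayed and descriptively summarized". A reader could therefore look for a pattern, although neither output corrects the Day 7 estimate.

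The single-score rule is worded for a missing score, and an unscheduled evening rating is not strictly missing. That is fair, but the plan then has no explicit rule for a morning-only day, and the morning score is still the only Day 7 value.

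A reader might infer that the whole post-infusion diary result is shifted. The documents do not support that: estimates are by day, no six-day average is specified in the visible text, and Days 2 to 6 carry no systematic offset. A reader might also infer that a clinic rating on Day 7 produces the same time-of-day error. That overlooks the in-clinic baseline rule, so that case is a conflict between two rules.

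**Conclusion.** The inconsistency is certain: the current text gives different accounts of Day 7 frequency and setting, and of the baseline if the rating is in clinic. The bias is conditional. It needs a remote morning-only rating, the SAP 9.1 baseline, and morning and evening ratings that differ on average. The Day 7 mean change is then off by about −D/2, and Hedges' g and the Day 7 LS mean are affected accordingly. If both Day 7 ratings are collected remotely, this systematic error does not arise. It would be too strong to say that the Day 7 result is biased, because D is unknown and may be zero. Severity is minor. It is worth correcting because the remedy uses data already planned.

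**What to change.** Reconcile Day 7 VAS frequency, setting and baseline across Protocol Table 3 and its VAS footnote, Protocol 7.1, 13.3 and 13.5, SAP 4.1, 7.2.1 and 9.1, and SAP Appendix B and its VAS footnote.

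- **If Day 7 is remote and morning-only:** keep the planned Days 2 to 7 model. Also report the Day 7 change and Hedges' g as the Day 7 morning rating against the participant's mean Day -7 to -1 morning rating. Footnote the Day 7 LS mean and its plotted point as resting on a mixed baseline. Record the change in SAP section 12.
- **If Day 7 is rated in clinic:** state which one baseline applies, and do not pool the rating with the remote daily means without saying so. The visit may fall on Day 6 or Day 8 and SAP 7.4 has no windowing, so also say which rating counts as Day 7.

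The cost is SAP wording, one derived variable and no new data. The morning baseline uses up to 7 ratings instead of 14, which raises the SD of the Day 7 change by about 3% with complete ratings. At the 10-of-14 minimum the rise is about 4% on average and at most 9.5%. Day 7 also carries a second estimate, on a different baseline from Days 2 to 6, and the tables must label it as such.

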4.3. Determination of Sample Size

Up to 24 participants will be dosed to achieve approximately 20 study completers, assuming a 20% study discontinuation rate among dosed participants.

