For each component, a mixed-effects model for repeated measures will be considered. Each repeated measures model will include (a) change from baseline scores as the dependent variable and (b) both baseline VAS component value and visit as fixed effect independent variables. The residual errors from the same participant across visits will be modeled using an unstructured covariance matrix (UN). If the model using an unstructured covariance matrix does not converge, compound symmetry (CS) and first order autoregressive (AR(1)) covariance structures may be used, in that order. Model-based point estimates (i.e., least squares means, their 95% confidence intervals (CIs), and standard errors (SEs) will be reported. For Day 1 the repeated timepoint will be hours and for Days 2 through 7 the repeated timepoint will be days.

Example SAS code:

Line plots of least squares (LS) mean will be plotted with standard error bars. Q-Q plot for residuals will also be provided to assess normality assumptions.

Listings of observed raw scores and change from baseline values will be presented separately for each VAS component by participant.

_	

	_
	_
	4
	-
	_
	ı
	i
	
	_
	_
	-
	-

10. Safety

The Safety Set (SS) will be used for all safety analyses. Safety and tolerability of brexanolone will be evaluated by incidence of treatment-emergent adverse events

Listings for discharge and safety phone call will also be included.

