10.5. Physical Examination

Physical examinations will include assessments of body systems (e.g., head, eye, ear, nose, and throat; heart; lungs; abdomen; and extremities) as well as cognitive and neurological examination and mental status examination, as performed per local standard of care. Unscheduled physical examinations may also be conducted per the investigator's discretion.

Any abnormality in physical examinations will be interpreted by an investigator as abnormal NCS or abnormal CS in source documents.

Physical examination performed (Yes/No), not done reason, date and time of the examination will be listed.

			_	
	1			
		 		_

11. **Interim Analyses**

There is no formal interim analysis planned for this study.

12. Changes from Analysis Planned in Protocol

Approximately 10 participants will be dosed instead of the expected 24 participants from the protocol.

A screened analysis set will be identified to include all participants who were screened for participation in this study. This analysis set will be used in a listing of inclusion and exclusion criteria violations, including the primary reason for exclusion.

An enrolled analysis set will be identified to include all participants who provided written informed consent and passed the inclusion and exclusion criteria for study participation. Screen failures will not be included in this set. This analysis set will be used to list protocol deviations.

13. Reference List

	I
	=

Statistical Analysis Plan for Interventional Studies
Sponsor: Sage Therapeutics, Inc.; Protocol No.: 547-TRM-201

14. Quality Control

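### The SAP's 95% CI for Hedges' g is too narrow when the baseline/post-baseline correlation is high and the effect is not small, because 2(1−r) also multiplies the d² term

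*SAP*

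**What the plan says.** SAP 9.1 adds a standardised pre-post effect size to the descriptive VAS summaries: "Considering the small sample size, unbiased Hedge's g will be used to compare the effect size of the post baseline score at each timepoint". The comparison is with the baseline score, separately for VAS-L and VAS-A.

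- The standardiser is SD_within = SD_CFB / √(2(1−r)), where "r is the correlation between baseline and post-baseline, n is the number of pairs".
- d is the mean difference divided by SD_within, and g = d × J with J = 1 − 3/(4(2n−2)−1).
- "The 95% CI of Hedge's g will be calculated as" g ± t(n−1, 0.025) × SE(g), with Var(d) = (1/n + d²/2n) × 2(1−r). In the text as read, J² stands outside the square root.

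On sample size, SAP 4.3 says "Up to 24 participants will be dosed to achieve approximately 20 study completers, assuming a 20% study discontinuation rate among dosed participants", while SAP 12 says "Approximately 10 participants will be dosed instead of the expected 24 participants from the protocol". Neither document gives a value for r or an expected effect on the VAS.

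**The concern.** Var(d) has two sources. One is sampling error of the mean change, which in SD_within units has variance 2(1−r)/n and rightly shrinks as r rises. The other is sampling error of SD_within, which enters in proportion to d². The SAP multiplies both by 2(1−r), so its second term is d²(1−r)/n and goes to zero as r approaches 1. The real uncertainty in SD_within does not.

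The intervals are therefore too narrow when participants keep their rank order (high r) and the shift is moderate or large, which is the case in which a reader would most want to rely on g. The plan produces 26 such intervals: seven Day 1 timepoints plus six days (Days 2 to 7), for two scales. They include Hour 6, a named secondary endpoint. In an open-label, single-arm study, a standardised effect with a tight CI is easily carried forward as evidence of the size of a signal.

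**Working it through.** **Inputs.** From SAP 9.1: 95% level, t(n−1, 0.025), and the formulas for d, J, SD_within and Var(d). From SAP 12: n of about 10. From SAP 4.3: about 20 completers, up to 24 dosed. Assumed, because the documents are silent: r from 0.3 to 0.95, true effect from 0 to 2 SD, bivariate normal scores, and equal SDs unless stated.

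**1. What the d² term should be.** To first order, with equal SDs and r estimated from the same pairs, SD_within² behaves like the mean of the two sample variances. Each has relative variance 2/(n−1), and their covariance is 2r²/(n−1). The relative variance of the mean is therefore (1+r²)/(n−1), and that of SD_within is (1+r²)/(4(n−1)). Hence

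Var(d) ≈ 2(1−r)/n + d²(1+r²)/(4(n−1)).

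**2. Coefficient of d² at n=10.**

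| r | SAP: (1−r)/10 | Approximation: (1+r²)/36 |
|---|---|---|
| 0.5 | 0.050 | 0.035 |
| 0.7 | 0.030 | 0.041 |
| 0.8 | 0.020 | 0.046 |
| 0.9 | 0.010 | 0.050 |

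They cross where 10r² + 36r − 26 = 0, so r = 0.617. For large n the condition is r² + 4r − 3 = 0, so r = √7 − 2 = 0.646.

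**3. One case by hand: n=10, r=0.9, d=0.8.** J = 1 − 3/71 = 0.958.

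- SAP: Var(d) = (0.1 + 0.64/20) × 0.2 = 0.0264, root 0.162. SE(g) is 0.156 with J and 0.149 with J².
- Corrected: 0.02 + 0.64 × 1.81/36 = 0.0522, root 0.228. SE(g) = 0.219.

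In simulation of this case the actual SD of g was 0.253. The median SE was 0.141 from the SAP formula with J² and 0.216 from the corrected one.

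**4. Coverage by simulation** (60,000 trials per cell, r estimated in each trial). The nominal 95% is met at zero effect: 95.2% to 97.3% for every r and n run. For n=10, using J:

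| True effect | r=0.5 | r=0.65 | r=0.7 | r=0.8 | r=0.9 |
|---|---|---|---|---|---|
| 0.5 | 96.2% | 95.0% | 94.5% | 92.8% | 88.7% |
| 0.8 | 95.3% | 93.6% | 92.6% | 89.7% | 82.1% |
| 1.0 | 94.8% | 92.8% | 91.6% | 87.7% | 78.4% |

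With J² the figures are about 0.3 to 2 points lower. More participants do not cure the problem: at effect 1.0 and r=0.9, coverage is 80.0% for n=20 and 80.1% for n=24.

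**5. Is the d² term the cause?** Removing 2(1−r) from that term alone, so that Var(d) = 2(1−r)/n + d²/(2n), gives 94.9%, 94.2% and 93.0% at r=0.7, 0.8 and 0.9 (n=10, effect 1.0). The SAP's formula gave 91.6%, 87.7% and 78.4%. Nearly all of the shortfall goes.

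**6. Unequal SDs** (post-baseline SD 0.7 times baseline, n=10, r=0.9, shift 0.8 baseline SD). Coverage is 70.9% with the SAP formula and J², 85.6% with the corrected closed form and 92.8% with a delete-one jackknife. Part of this loss comes from the unequal SDs and not from the d² term.

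**The case against.** The strongest reply is that nothing in the documents places the trial in the affected region, since r and the effect are unknown. Up to r=0.65 and effects of 0.8, coverage is at least about 93%. Just above 0.65 the loss is modest, and it becomes material only from r of about 0.8. That stands. High r is plausible, because Day 1 ratings follow the predose rating within hours and the remote baseline averages up to 14 ratings, but this is inference.

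The position of J² may come from the PDF reading. This is also fair, but it moves coverage by at most about 2 points and does not explain the shortfall.

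The intervals are descriptive. The primary endpoint is TEAE incidence, no decision rule uses g, and inference on mean change comes from the mixed model: "Model-based point estimates (i.e., least squares means, their 95% confidence intervals (CIs), and standard errors (SEs) will be reported". At zero effect the CI is sound, so it does not manufacture an effect. It overstates how precisely a real one is known. All of this limits the consequence without removing the error.

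The SAP cites a published source for its formula. A citation does not change the coverage.

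The corrected coefficient is itself a normal-theory, equal-SD approximation. Using 4n in place of 4(n−1) gives 0.045 at r=0.9 and n=10, so the SAP's coefficient is about 4.5 to 5 times too small.

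**Conclusion.** The concern holds. The SAP's variance formula shrinks a component that does not shrink with r, and the resulting CI undercovers when r is high and the effect is not small. The d² coefficients cross at r of about 0.65 (0.62 at n=10). The loss becomes material from about r=0.8 with an effect of 0.5 SD or more, and reaches 13 points at r=0.9 and effect 0.8 (95% nominal against 82.1%, n=10, J reading). At r of about 0.5 or less the interval is adequate or conservative, except for very large effects (93.7% at effect 2.0, r=0.5). These figures rest on bivariate normal scores with equal SDs and on assumed values of r and effect. The matter should be corrected, but it is confined to the descriptive intervals for g.

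**What to change.** Preferred: keep g ± t(n−1, 0.025) × SE(g), but compute SE(g) by the jackknife, leaving out one participant at a time. It needs neither equal SDs nor normal theory. It covered 92% to 97% in every setting tried: n=8, 10 and 20; SD ratios 0.7, 1 and 1.3; and scores rounded and clipped to 0–100.

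If a closed form is wanted, use SE(g) = J × √[2(1−r)/n + d²(1+r²)/(4(n−1))] and state the assumption of roughly normal scores with similar SDs. With equal normal SDs at n=10 it covers 92.9% to 97.5%. The smallest edit, taking 2(1−r) off the d² term only, performs almost as well with equal SDs. Closed forms still undercover when the SDs differ.

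In either case, confirm that the program multiplies √Var(d) by J and not J², and report r beside each g.

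The cost is one sentence in SAP 9.1 and a short loop or one formula in the program, with no new data. Intervals will be wider when r is high: at n=10, r=0.9 and effect 0.8, the median half-width is 0.32 as printed, 0.49 with the closed form and 0.55 with the jackknife. The jackknife fails if leaving out one participant makes all remaining post-baseline scores identical. This happened in about 32% of trials in an extreme floor case (assumed mean 25, SD 20, shift 2 SD) and in 0% to 0.2% in milder ones. The SAP should say that g is then reported without a CI.

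### SAP 9.1 puts J² where its own definition of Hedges' g requires J in the standard error, so the effect-size intervals come out slightly too narrow (4.2% at 10 pairs)

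*SAP*

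**What the plan says.** SAP Section 9.1 gives the small sample as its reason for adding Hedges' g to the descriptive statistics for each VAS component. It defines g = d × J. Here d is the mean change divided by a within-participant SD, J = 1 − 3/(4(2n − 2) − 1), and "r is the correlation between baseline and post-baseline, n is the number of pairs".

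The interval is introduced with "The 95% CI of Hedge's g will be calculated as" and takes the form g ± t(n − 1, 0.025) × SE(g). In the supplied text, which carries the equation as typesetting code, the standard error is "SE(g) = \sqrt{Var(g)} = \sqrt{Var(d)} \times J^2". The expanded version that follows ends "1}{n} + \frac{d^2}{2n}\right)2(1-r)} \left(1 - \frac{3}{4(2n-2)-1}\right)^2". In both, the root closes before the squared correction factor: after Var(d) in the first and after 2(1 − r) in the second.

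On sample size, SAP Section 12 states "Approximately 10 participants will be dosed instead of the expected 24 participants from the protocol". SAP Section 4.3 still carries the protocol's planning assumption, "assuming a 20% study discontinuation rate among dosed participants".

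**The concern.** For a given n, J is a constant. Multiplying d by J multiplies its variance by J² and its standard error by J. The printed line carries the J² that belongs to the variance over to the standard error, so its two sides agree only if J = 1, which no finite n gives.

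A programmer who follows the line literally will shorten every Hedges' g interval. A second programmer checking against the same SAP could reproduce the error. Section 9.1 covers seven Day 1 time points and six daily means (Days 2 to 7) for two scales, so (7 + 6) × 2 = 26 intervals are involved. The shortfall grows as n falls, so it is larger at about 10 dosed than at the roughly 20 completers first planned.

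**Working it through.** The documents state no numerical SE, interval width or precision target, so there is no plan figure to reproduce. The check is algebra followed by size.

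**Inputs.** From SAP 9.1: g = d × J; J = 1 − 3/(4(2n − 2) − 1); Var(d) = (1/n + d²/(2n)) × 2(1 − r); multiplier t(n − 1, 0.025); n is the number of pairs. From SAP 12: about 10 dosed. From SAP 4.3: 20% discontinuation. Assumed, because the documents give no values: d = −0.5 and r = 0.5 for the worked example, and 8 pairs as 10 × 0.8.

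**Algebra.** Var(g) = Var(d × J) = J² × Var(d). Hence SE(g) = sqrt(J² × Var(d)) = J × sqrt(Var(d)). The printed form is J² × sqrt(Var(d)). Printed divided by implied is J, whatever d and r are.

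**Size of J.**
- n = 8: 1 − 3/55 = 0.9455, so 5.5% too narrow
- n = 10: 1 − 3/71 = 0.9577, so 4.2% too narrow
- n = 20: 1 − 3/151 = 0.9801, so 2.0% too narrow

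**Worked example, n = 10, d = −0.5, r = 0.5.** sqrt(Var(d)) = sqrt((0.1 + 0.25/20) × 2 × 0.5) = 0.3354, and g = −0.5 × 0.9577 = −0.479.
- As printed: SE = 0.9577² × 0.3354 = 0.3077; half-width = 2.262 × 0.3077 = 0.696; interval −1.17 to 0.22.
- As implied by g = d × J: SE = 0.9577 × 0.3354 = 0.3212; half-width = 2.262 × 0.3212 = 0.727; interval −1.21 to 0.25.

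At n = 8 with the same d and r, the half-widths are 0.793 and 0.838.

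**Coverage.** Paired normal data with equal SDs were simulated with r estimated from each sample, using 60,000 to 100,000 data sets per setting (Monte Carlo error about 0.1 point). Some results, in per cent:

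| n | r | true effect | printed (J²) | corrected (J) |
|---|---|---|---|---|
| 10 | 0.3 | −0.5 | 96.2 | 96.9 |
| 10 | 0.5 | −0.5 | 95.2 | 96.0 |
| 10 | 0.7 | −0.5 | 93.6 | 94.4 |
| 10 | 0.7 | −1 | 90.7 | 91.7 |
| 10 | 0.8 | −1 | 86.5 | 87.7 |
| 8 | 0.5 | −1 | 93.2 | 94.2 |
| 8 | 0.8 | −1 | 85.0 | 86.6 |
| 20 | 0.3 | −1 | 96.6 | 96.9 |

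The printed interval always covers less, by about 0.3 to 1.3 points for r of 0.3 to 0.7 and by up to about 1.6 points at r = 0.8.

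**The case against.** The strongest objection is that the SAP may not contain the error. Everything turns on where a root sign ends, and the equation was read from PDF by a program. If the sign on the original page covers J², the line is sqrt(Var(d) × J²), which is correct. That the two displayed forms agree is only modest evidence, since one misreading could affect both. This stands as a condition: the supplied text can be judged, the original page cannot.

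The second objection concerns consequence. A reader might infer that the printed intervals fall below 95% coverage and that the correction restores it. The simulations do not support that. Over n = 8, 10 and 20, r = 0.3, 0.5 and 0.7, and effects of −0.25, −0.5 and −1, the printed interval was closer to 95% than the corrected one in 19 of 27 settings, because the corrected one is often conservative. Where coverage is poor, the J² is not the main cause: at n = 10, r = 0.7 and an effect of −1, the fix recovers one point (90.7% to 91.7%) of a shortfall of more than four. The rest comes from some other feature of the interval, which is a separate question.

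Third, the SAP attaches no test, threshold or decision to Hedges' g. The repeated-measures model in Section 9.1 supplies its own least squares means, standard errors and intervals.

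Fourth, 8 pairs is an illustration. Pairs are counted at each time point, and a study discontinuation rate need not describe losses during a six-hour infusion.

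These objections limit the point to a minor one. None makes the printed equality true.

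**Conclusion.** The point holds as a minor error in a prespecified formula. As supplied, the SE line in SAP 9.1 is inconsistent with the SAP's own definition of g. Coded literally, it understates each SE and half-width by the factor J: 4.2% at 10 pairs, 2.0% at 20, and 5.5% if only 8 pairs remain. Too narrow here means relative to the SE that g = d × J implies; it does not mean that the intervals are shown to miss nominal coverage. At r of 0.5 or less, both versions are near or above 95% in most settings tried.

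A reader might also infer that the reported effect sizes or the secondary efficacy analysis are wrong. They are not affected by this: g, the repeated-measures results and the primary endpoint (incidence of TEAEs) do not use this standard error. The conclusion depends on the root on the source page ending where the supplied text shows it. The coverage figures depend on normal paired data with equal SDs and on the assumed values of r and d.

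**What to change.** Look at the equation on the source page of SAP 9.1. If J² lies outside the root, replace the line with SE(g) = sqrt(J² × Var(d)) = J × sqrt(Var(d)), and correct the expanded form in the same way, so that the bracketed factor outside the root appears to the first power. If the root already covers J², the SAP needs no change. In either case, confirm that the production and checking programs use J to the first power outside the root.

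The cost is one SAP line and one code line, with no effect on design or data collection. Corrected intervals are wider by 1/J − 1: 1/0.9577 − 1 = 4.4% at 10 pairs and 1/0.9455 − 1 = 5.8% at 8.
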